8.1. Efficacy Assessments

8.1.1. Tumor Response Assessments

Tumor assessments will include all known or suspected disease sites. Imaging will include contrast enhanced chest, abdomen and pelvis CT or for participants with known CT contrast allergy, a non-contrast CT of the chest with contrast enhanced abdominal and pelvic MRI; brain CT or MRI scan for participants with known or suspected brain metastases; bone scan and/or bone x-rays for participants with known or suspected bone metastases. CT/MRI imaging of other areas of tumor involvement not listed above should also be reported. The same imaging technique used to characterize each identified and reported lesion at baseline will be employed in the following tumor assessments. It is important to use the same technique, especially if using non-contrast computed tomography of the chest and MRI of abdomen and pelvis for those with contrast allergy.

Anti-tumor activity will be assessed through radiological tumor assessments conducted at baseline, during treatment as specified in the [SoA](#), whenever disease progression is suspected (eg, symptomatic deterioration), and at the time of withdrawal from treatment (if not done in the previous 6 weeks). Assessment of response will be made using RECIST version 1.1 ([Appendix 11](#)). Tumor response assessment will be performed locally.

All participants' files and radiologic images must be available for source verification and for potential peer review.

For Part 2 Dose Expansion, radiologic images will be submitted to an imaging laboratory for the purpose of holding for possible future central review if deemed necessary. In the event that central review is conducted, it would not be a complete medical review of participant and no incidental findings will be shared with the PI, site staff, or participant. All safety reviews will be the sole responsibility of the site staff.

Detailed information regarding the submission of images to the core laboratory is found in the Imaging Manual.

8.2. Safety Assessments

Planned time points for all safety assessments are provided in the [SoA](#). Unscheduled clinical laboratory measurements may be obtained at any time during the study to assess any perceived safety issues.

Safety assessments will include collection of AEs, SAEs, vital signs and physical examination, ECG (12-lead), laboratory assessments, including pregnancy tests and verification of concomitant treatments.

8.2.1. Physical Examinations

Participants will have a physical examination to include weight, assessment of ECOG performance status and height; height will be measured at baseline only.

A complete physical examination will include, at a minimum, assessments of the eyes, ears, nose, throat, heart, lungs, abdomen, skin, and neurologic system.

A brief physical examination will include, at a minimum, assessments of the heart, lungs, and abdomen including skin at injection sites.

Investigators should pay special attention to clinical signs related to previous serious illnesses.

8.2.2. Vital Signs

Temperature (oral preferred), heart rate, and BP will be assessed.

Blood pressure and heart rate measurements will be assessed in the sitting or semi-supine position with a completely automated device. Manual techniques will be used only if an automated device is not available.

Blood pressure and heart rate measurements should be preceded by at least 5 minutes of rest for the participant.

Vital signs (to be taken before blood collection for laboratory tests) will consist of 1 heart rate and 3 blood pressure measurements (during screening). The average of the 3 blood pressure readings will be recorded on the CRF.

8.2.3. Electrocardiograms

Standard 12-lead ECGs utilizing limb leads (with a 10-second rhythm strip) should be collected at times specified in the **SoA** section of this protocol using an ECG machine that automatically calculates the heart rate and measures PR, QT, and QTcF intervals and QRS complex. Alternative lead placement methodology using torso leads (eg, Mason-Likar) is not recommended given the potential risk of discrepancies with ECGs acquired using standard limb lead placement. All scheduled ECGs should be performed after the participant has rested quietly for at least 10 minutes in a supine position.

At each time point (see the schedule of activities), 3 consecutive ECGs will be performed at approximately 1-4 minutes apart to determine the mean QTcF interval. To ensure safety of the participants, a qualified individual at the investigator site will make comparisons to baseline measurements. Additional ECG monitoring will occur if a) the mean value from the triplicate measurements for any postdose QTcF interval is increased by ≥ 60 msec from the baseline **and** is >450 msec; or b) an absolute QTcF value is ≥ 500 msec for any scheduled ECG. If either of these conditions occurs, then a single ECG measurement must be repeated at least hourly until QTcF values from 2 successive ECGs fall below the threshold value that triggered the repeat measurement. In addition, if verified QTcF values continue to exceed the criteria above, immediate correction for reversible causes including electrolyte abnormalities, hypoxia and concomitant medications for drugs with the potential to prolong the QTcF interval should be performed. Consultation with a cardiologist will be performed if clinically warranted or if the QTcF value is >500 msec for any scheduled ECG.

If the QTcF interval reverts to less than the threshold criteria listed above, and in the judgment of the investigator(s) and sponsor, it is determined that the cause(s) of QTcF prolongation is something other than study intervention, treatment may be continued with regular ECG monitoring. If in that timeframe the QTcF intervals rise above the threshold values, the study intervention will be held until the QTcF interval decreases to below the threshold values. Participants will then restart the study intervention at the next lowest dose level. If the QTcF interval has still not decreased to 480 msec after 2 weeks, or if at any time a participant has a QTcF interval >515 msec attributed to study treatment or becomes symptomatic due to QTcF changes, the participant will be removed from the study. Additional triplicate ECGs may be performed as clinically indicated.

In some cases, it may be appropriate to repeat abnormal ECGs to rule out improper lead placement as contributing to the ECG abnormality. It is important that leads be placed in the same positions each time in order to achieve precise ECG recordings. If a machine-read QTcF value is prolonged, as defined above, repeat measurements may not be necessary if a qualified medical provider's interpretation determines that the QTcF values are in the acceptable range.

If a participant experiences a cardiac or neurologic AE (specifically syncope, dizziness, seizures, or stroke), an ECG (triplicate) should be obtained at the time of the event.

ECG values of potential clinical concern are listed in [Appendix 7](#).

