7. DISCONTINUATION OF STUDY INTERVENTION AND PARTICIPANT DISCONTINUATION/WITHDRAWAL

7.1. Discontinuation of Study Intervention

In rare instances, it may be necessary for a participant to permanently discontinue study intervention (definitive discontinuation). Reasons for definitive discontinuation of study intervention may include the following:

- Objective disease progression;
- Global deterioration of health status requiring discontinuation;
- Unacceptable toxicity;
- Pregnancy;
- Significant protocol violation;
- Lost to follow-up;

- Participant refused further treatment;
- Study terminated by sponsor;
- Death.

Note that discontinuation of study intervention does not represent withdrawal from the study. If study intervention is definitively discontinued, the participant will remain in the study to be evaluated for long-term safety follow-up and survival. See the [SoA](#) for data to be collected at the time of discontinuation of study intervention and follow-up for any further evaluations that need to be completed.

In the event of discontinuation of study intervention, it must be documented on the appropriate CRF/in the medical records whether the participant is discontinuing further receipt of study intervention or also from study procedures, posttreatment study follow-up, and/or future collection of additional information.

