7.2. Participant Discontinuation/Withdrawal From the Study

A participant may withdraw from the study at any time at his/her own request. Reasons for discontinuation from the study may include:

- Completed study follow-up;
- Study terminated by sponsor;
- Lost to follow-up;
- Refused further follow-up;
- Death.

At the time of discontinuing from the study, if possible, an early discontinuation visit should be conducted. See the [SoA](#) for assessments to be collected at the time of study discontinuation and follow-up and for any further evaluations that need to be completed.

If a participant withdraws from the study, he/she may request destruction of any remaining samples taken and not tested, and the investigator must document any such requests in the site study records and notify the sponsor accordingly.

If the participant withdraws from the study and also withdraws consent (see Section 7.2.1) for disclosure of future information, no further evaluations should be performed and no additional data should be collected. The sponsor may retain and continue to use any data collected before such withdrawal of consent.

Lack of completion of all or any of the withdrawal/early termination procedures will not be viewed as protocol deviations so long as the participant's safety was preserved.

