8.3.3. Follow-up of AEs and SAEs

After the initial AE/SAE report, the investigator is required to proactively follow each participant at subsequent visits/contacts. For each event, the investigator must pursue and obtain adequate information until resolution, stabilization, the event is otherwise explained, or the participant is lost to follow-up (as defined in [Section 7.3](#)).

In general, follow-up information will include a description of the event in sufficient detail to allow for a complete medical assessment of the case and independent determination of

possible causality. Any information relevant to the event, such as concomitant medications and illnesses, must be provided. In the case of a participant death, a summary of available autopsy findings must be submitted as soon as possible to Pfizer Safety.

Further information on follow-up procedures is given in [Appendix 3](#).

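### Protocol 8.2.3 removes participants who meet a QTcF trigger from the study, which conflicts with Section 7.1 and could end survival contacts and late SAE elicitation

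*Protocol*

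**What the plan says.** Protocol 8.2.3 attaches one action to three alternative triggers: QTcF still not down to 480 msec after 2 weeks; QTcF above 515 msec at any time and attributed to study treatment; or symptoms. The sentence closes "or becomes symptomatic due to QTcF changes, the participant will be removed from the study". Earlier in the same paragraph the drug is named separately: "the study intervention will be held until the QTcF interval decreases to below the threshold values".

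Protocol 7.1 lists unacceptable toxicity among the reasons for stopping study intervention permanently. It adds "Note that discontinuation of study intervention does not represent withdrawal from the study", and after a permanent stop "the participant will remain in the study to be evaluated for long-term safety follow-up and survival".

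Protocol 7.2 covers leaving the study. Its list, introduced by "Reasons for discontinuation from the study may include", names completed follow-up, sponsor termination, loss to follow-up, refusal of further follow-up, and death.

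**The concern.** The two instructions differ on what happens after a serious QTcF finding. Under 7.1 the participant stops drug and stays under observation. Under 8.2.3, read as written, the participant leaves the study. This is an operative rule in a first-in-human trial, and it applies to participants with a cardiac signal, in whom late safety information matters most.

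Two activities depend on continued participation: the survival contact every 8 weeks until study end (8.2.12), and the active elicitation of SAEs during long-term follow-up once the 90-day window has closed (8.3.1). If a site stops them because of toxicity, late SAEs may be missed and survival follow-up may end for a reason that is not independent of prognosis.

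**Working it through.** No sample size, power or error rate is involved. The check sets the sections side by side.

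1. **The action.** All three triggers in 8.2.3 lead to removal from the study. The paragraph uses a different term when it means the drug, so a site can reasonably take the two terms to mean different things.

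2. **Against 7.1.** A QTcF trigger attributed to treatment falls naturally under unacceptable toxicity. Section 7.1 then keeps the participant in the study. Both instructions are mandatory, and they cannot both be followed literally.

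3. **Against 7.2.** No listed reason for leaving the study is a toxicity. The list is open-ended, however, so it does not forbid removal. The direct conflict is with 7.1.

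4. **Against the other toxicity rules.** Section 6.6.3 (more than one dose reduction) takes the participant off treatment and into the follow-up phase. Section 6.5.11.3 (hypersensitivity) allows the drug to be stopped, with follow-up to study end. Appendix 14 (immune-mediated myocarditis) and Appendix 15 (Grade 3 or 4 infusion reactions) stop treatment permanently. None of these ends study participation.

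5. **What is kept and what is exposed.**

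| Activity | Position after removal under 8.2.3 |
|---|---|
| AE/SAE collection to 90 days after last dose | Protected: 8.3.1 gives early ends only for screen failure and withdrawn consent |
| Follow-up of the QTcF event | Protected: 8.3.3 says "the investigator must pursue and obtain adequate information until resolution, stabilization, the event is otherwise explained, or the participant is lost to follow-up" |
| Related SAE that the investigator later learns of | Still reportable (8.3.1) |
| Active SAE elicitation after 90 days | Exposed: 8.3.1 lifts the duty to seek events once participation has concluded |
| Survival contact every 8 weeks | Exposed (8.2.12) |

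6. **Effect on overall survival.** OS is a secondary, descriptive endpoint in Part 2 only. Protocol 9.4.2 analyzes it in the Response Evaluable Set, which needs at least one post-baseline disease assessment. SAP Table 5 censors living participants at last contact and counts a death as an event. If contacts stop and nothing further is learned, censoring comes earlier.

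7. **Who may fall outside the OS set.** Take a participant removed after the first dose only. The first scheduled scan is at week 8 (± 7 days). The end-of-treatment visit is at most 28 days after last dose, and a scan is due there only if more than 6 weeks (42 days) have passed since the previous one. At a day-28 visit a scan is therefore due only if the baseline scan was more than 42 − 28 = 14 days before first dose. Otherwise there may be no post-baseline scan, and the possible loss is confined to late SAE elicitation. The same holds in Part 1, where OS is not an endpoint.

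8. **Size.** The number affected is the trigger rate times the number treated. Planned enrollment is 74 to 172, but neither document gives a trigger rate, so the product cannot be formed.

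**The case against.** The best reply is that, read as a whole, the protocol means removal from treatment. The opening of Section 8 sends safety issues to the sponsor at once, to decide whether study intervention continues, so the decision there concerns drug. Section 7.2 refers sites to the Schedule of Activities "for assessments to be collected at the time of study discontinuation and follow-up and for any further evaluations that need to be completed", and it bars further data collection only in the case that begins "If the participant withdraws from the study and also withdraws consent". Section 7.2.1 keeps participants who ask to stop drug in follow-up unless they refuse contact. Section 8.2.12 has no exception for removed participants. On this view, harm needs a site to follow one sentence against several others and the sponsor not to correct it.

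Much of this stands. It shows what was probably intended, and it makes the consequence conditional. It does not remove the conflict. Section 7.2.1 is written for participants who ask to stop, not for those removed by the investigator, and none of the other text says that it prevails over 8.2.3.

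Two stronger readings fail. A reader might infer that removed participants lose all safety follow-up; 8.3.1 and 8.3.3 show otherwise. A reader might also infer that they would necessarily be censored early for OS. A known death is still an event under SAP Table 5, and 7.2.1 allows publicly available information on vital status to be used, subject to local law. Ending the calls does not by itself fix the censoring date.

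**Conclusion.** The conflict between 8.2.3 and 7.1 is real, and no text expressly resolves it. The consequence is a risk: loss of survival contacts and of active SAE elicitation after 90 days, if a site follows 8.2.3 literally and is not corrected. In Part 2 this could bring earlier, toxicity-linked OS censoring for those in the Response Evaluable Set, unless death is learned by other means. No primary endpoint is affected.

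The size cannot be derived and is probably small. A reader might infer from the Section 1.3 note on the C3D1 electrocardiogram that scheduled ECGs end there, and so confine detection to about 8 weeks. The documents do not support that. Section 1.3.2 has its own electrocardiogram row, whose entries cannot be read in the available text. The vital-signs row beside it is also blank, although vital signs are required at the 1-month visit. Section 8.2.3 also calls for continued ECG monitoring after a QTcF event in some cases, and for ECGs at certain cardiac or neurologic events. A count of missed contacts would be no more useful, since it would describe one hypothetical survivor and could be 0.

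Severity: minor. Confidence is high in the textual conflict and lower in any practical effect.

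**What to change.** In Protocol 8.2.3, replace the removal phrase with *permanently discontinued from study intervention and followed per Section 7.1 and the SoA (Section 1.3.2)*. Leave the QTcF thresholds unchanged. Section 6.6.3 already uses wording of this kind.

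The cost is one phrase in the next amendment. It adds no visit or contact beyond those already scheduled for every other participant who stops drug, and the SAP needs no change.

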8.2.4. Echocardiogram or MUGA

Participants must be in supine position in a rested and calm state for at least 5 minutes before LVEF assessment is conducted. If the participant is unable to be in the supine position, the participant should be in the most recumbent position possible.

The investigator or designated site physician will review all echocardiograms. Once signed, the original echocardiogram will be retained with the participant's source documents. At the request of the sponsor, a copy of the original echocardiogram will be made available to Pfizer. Standard echocardiogram machines should be used for all study-related echocardiogram requirements.

Echocardiograms or MUGAs (preferred) will be measured at time points specified in the [SoA](#) or if clinically warranted. Imaging method must be consistent throughout the study for individual participants.

8.2.5. Clinical Safety Laboratory Assessments

See [Appendix 2](#) for the list of clinical safety laboratory tests to be performed and the [SoA](#) for the timing and frequency. All protocol required laboratory assessments, as defined in [Appendix 2](#), must be conducted in accordance with the laboratory manual and the [SoA](#). Unscheduled clinical laboratory measurements may be obtained at any time during the study to assess any perceived safety issues.

The investigator must review the laboratory report, document this review, and record any clinically relevant changes occurring during the study in the AE section of the CRF. Clinically significant abnormal laboratory findings are those which are not associated with the underlying disease, unless judged by the investigator to be more severe than expected for the participant's condition.

All laboratory tests with values considered clinically significantly abnormal during participation in the study or within 28 days after the last dose of study intervention should be repeated until the values return to normal or baseline or are no longer considered clinically significant by the investigator or medical monitor.

If such values do not return to normal/baseline within a period of time judged reasonable by the investigator, the etiology should be identified, and the sponsor notified.

See [Appendix 6](#) for suggested actions and follow-up assessments in the event of potential drug-induced liver injury.

8.2.6. Safety Imaging Assessments

Not applicable. Refer to [Section 8.1.1](#) for efficacy imaging.

8.2.7. Pregnancy Testing

Pregnancy tests may be urine or serum tests, but must have a sensitivity of at least 25 mIU/mL. Pregnancy tests will be performed in WOCBP at the times listed in the [SoA](#). Following a negative pregnancy test result at screening, appropriate contraception must be

commenced, and a second negative pregnancy test result will be required at the baseline visit prior to the participant's receiving the study intervention. Pregnancy tests will also be done whenever 1 menstrual cycle is missed during the active treatment period (or when potential pregnancy is otherwise suspected) and at the end of the study. Pregnancy tests may also be repeated if requested by IRBs/ECs or if required by local regulations. If a urine test cannot be confirmed as negative (eg, an ambiguous result), a serum pregnancy test is required. In such cases, the participant must be excluded if the serum pregnancy result is positive.

8.2.8. Fertility Perservation

Male participants planning to have children in the future should consider banking their sperm prior to starting the study. These discussions must take place prior to enrollment as sperm donations during or after the study are not recommended. Highly effective contraceptive precautions should be used to prevent pregnancy when either partner is receiving PF-07209960 as described in [Appendix 4](#).

8.2.9. Inpatient Monitoring

Participants receiving PF-07209960 will be monitored (per local standard of practice) during and following their first dose with a 72-hour inpatient hospitalization period. This will be implemented throughout dose escalation, and length of inpatient hospitalization will be re-assessed based on safety data prior to starting dose expansion cohorts. Participants should remain at the investigational site for observation for at least 1-hour post dose for all treatment visits after C1D1. For C1D15 PF-07209960 IV administration, participants should remain at the investigational site for observation for at least 8-hours post dose. Participants may not be released until the investigator has confirmed the participant has not exhibited signs and symptoms of a cytokine reaction. Actual observation times for second and subsequent doses may be lengthened depending on clinical experience during hospitalization for previous doses. Participants may be released only after the investigator has confirmed the participant has sufficiently recovered from any CRS. Hospitalization period may be extended if the participant experiences abnormal laboratory findings or ongoing AEs that require further hospitalization. Participants should complete the required study specific laboratory assessments as detailed in the [SoA](#) and monitored per local standard practice for inpatient monitoring.

Record AEs (AEs consist of nonserious AEs and SAEs) as described in [Appendix 3](#).

Refer to [Appendix 9](#) for CRS Mitigation and Management guidance.

